#### 2.2.2 Study Device Contraindication

Patients with known sensitivity or allergy to porcine materials.

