#### 5.5 Screen Failures

Screen failures are defined as subjects created by the site on the Case Report Form (CRF) who do not meet one or more eligibility criteria for participation in the study. A minimal set of screen failure information is required to ensure transparent reporting of screen failure participants, to meet the Consolidated Standards of Reporting Trials (CONSORT) publishing requirements and to respond to queries from regulatory authorities. Minimal information to be collected on the CRF includes demography, screen failure details, eligibility criteria, and any serious adverse event (SAE). This will be documented on the Screening and Enrollment log.

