#### **5.6** Strategies for Recruitment

The retrospective chart review will include the full consecutive series of patients between 22 years and 80 years old who underwent abdominal wall reconstruction for a hernia with Integra Gentrix® Surgical Matrix during the time period between November 1, 2017, and present (90 days prior). Subjects from that consecutive series will be included in the study based on the defined inclusion and exclusion criteria. Collection of patients' data treated with the Gentrix® Surgical Matrix per routine/standard of care use and in accordance with the Instructions for Use (IFU).

The institutional charts from the study site will constitute the source documents, and data from such charts will be collected using a study-specific eCRF by the site responsible or their designee(s). Each patient should be included in the study only once. Patient screening will rely on manual selection of institutional charts or other means. In these cases, every effort should be made to identify every possible eligible patient. In order to be eligible for the study, patients should meet all of the eligibility criteria.

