#### 5.7.3 Anticipated Clinical and device Benefits

There is no direct benefit. Information learned from this study might help researchers to better understand medical treatments and disease processes or procedures in order to better help others in the future.

The data collected from the study will be used to inform the device manufacturer about the safety and performance of the device when used in accordance with the device labelling.

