# 6 Study Assessments and Procedures

#### 6.1 Schedule of Data Collection

### 6.1.1 Screening

- The procedures to be completed are:
  - ✓ Retrospective chart review will include the full consecutive series of patients between 22 years and 80 years old who underwent abdominal wall reconstruction for a hernia with Integra Gentrix® Surgical Matrixbetween November 1, 2017, and present (90 days prior).
  - ✓ Creation on the eCRF of a new case book for each eligible subject. Each created case book assigns the eligible subject with a study number.
  - ✓ Completion of Worksheets/ eCRFs: Site will transcribe/transmit the below-mentioned patients' data in study worksheets & eCRFs. The patients' data will originate from existing medical and other patient records.
- The patients' data to be collected are:
  - ✓ Eligibility:
    - o Inclusion Criteria: Ensure the subject meets the inclusion criteria.
    - o Exclusion Criteria: Ensure the subject does not meet any of the exclusion criteria.
  - ✓ Demographics: gender, year of birth, height, weight, race, ethnicity, nicotine and alcohol use history.
  - ✓ Medical history: Obtain subject 's medical history up to 3 years prior to surgery. Medical history is considered relevant when related to any of the study eligibility criteria, or when it may affect any of the clinical investigation endpoints, at the discretion of the investigator. Relevant medical history covers at a minimum Ventral Hernia related medical history treated in this study.

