#### 7. ANALYSIS POPULATION

**Enrolled**: The enrolled population includes all eligible subjects based on the defined inclusion and exclusion criteria.

**Intent-to-Treat (ITT) Population:** All subjects who are enrolled into the study, provide informed consent waiver, and receive study intervention.

**Per-Protocol (PP) Population**: All subjects in the full Analysis Set not identified as major protocol violations.

The endpoints analysis will be based on the Intent-To-Treat population. The per-protocol set will be supportive and will be used to assess the robustness of study results if neccesary. Safety analysis will be based on the Intent-To-Treat population.

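### Screen failures in this series already carry a Gentrix implant and their SAEs are to be recorded, yet no planned safety table or rate counts them

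*Protocol*

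**What the plan says.** **Who is screened.** Protocol 5.6 draws on the full consecutive series of patients aged 22 to 80 "who underwent abdominal wall reconstruction for a hernia with Integra Gentrix® Surgical Matrix during the time period between November 1, 2017, and present". Protocol 6.1.1 repeats this.

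**Who is a screen failure.** Protocol 5.5: "Screen failures are defined as subjects created by the site on the Case Report Form (CRF) who do not meet one or more eligibility criteria". It then sets the minimum data: "Minimal information to be collected on the CRF includes demography, screen failure details, eligibility criteria, and any serious adverse event (SAE". The stated reasons are transparent reporting, CONSORT and regulatory queries.

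**Who is analysed for safety.** The synopsis restricts analysis to evaluable subjects who meet the eligibility criteria. Protocol 10.3 uses the full analysis set of enrolled, treated subjects. SAP 7 says "Safety analysis will be based on the Intent-To-Treat population" and, of the enrolled set from which ITT is drawn, "The enrolled population includes all eligible subjects based on the defined inclusion and exclusion criteria".

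**What is reported on screen failures.** SAP 9.2.1 gives their number in the disposition summary. No other SAP output names them.

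**The concern.** In a prospective trial a screen failure is usually unexposed, so leaving it out of the safety set costs nothing. Here the operation precedes screening. An exclusion applied to a chart cannot change anyone's exposure; it decides whose events are summarised.

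Protocol 3.1 says that the study will confirm safety and detect side-effects not yet known. Protocol 2.3 places this in a real-world population, and Protocol 5.7.3 says that the data will inform the manufacturer about "safety and performance of the device when used in accordance with the device labelling". The only contraindication stated in the Protocol is "Patients with known sensitivity or allergy to porcine materials", which corresponds to exclusion 1. Exclusions 2 to 5 are not stated as contraindications.

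At stake is a report that gives a safety rate for Gentrix from about 35 patients while serious events recorded in other implanted patients of the same series enter no count.

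**Working it through.** **Step 1. Exposure.** The screened series is defined by having received Gentrix, so a patient who fails on exclusions 1 to 5 is implanted. The exception is a case opened in error, such as a patient who turns out not to have received the device.

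**Step 2. Safety sets, traced to their definitions.**

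| Place | Set named for safety | Contains recorded screen failures? |
|---|---|---|
| Synopsis, statistical methods | Evaluable and eligible (all analyses) | No |
| Protocol 10.3 | Full analysis set: enrolled and treated | No |
| SAP 7 | ITT, drawn from enrolled, defined as eligible | No |
| SAP 9.3.4 (device deficiencies) | Enrolled | No |
| SAP 9.3.5, first statement | Enrolled | No |
| SAP 9.3.5, second statement | A full analysis population that the SAP does not define | Cannot be determined |

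No defined set holds a patient recorded as a screen failure, and SAP 7 and 9.3.5 between them name three different sets for safety.

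**Step 3. Listings.** Protocol 10.4.1 and 10.4.10 promise listings of all collected data. Protocol 10.4.6 lists deaths and SAEs without naming a set in that sentence. SAP 9.3.5 lists deaths and SADEs, which drops SAEs judged unrelated to the device. Its AE listing has a seriousness field, but nothing says that it covers screen failures.

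**Step 4. Capture.** Protocol 5.5 needs a CRF entry for the ineligible patient. Against it:
- Protocol 5.4 starts data collection with the first patient who meets all criteria.
- Protocol 6.1.1 calls for "Creation on the eCRF of a new case book for each eligible subject".
- Protocol 7.3.1 collects AEs and SAEs for enrolled subjects, from enrollment on.

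A site following these three sections would not record what 5.5 requires.

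**Step 5. Scale, on assumed inputs only.** The one figure in the documents is the planned size, about 35 (Protocol 10.2, SAP 8), given without a calculation, so there is nothing to reproduce. Let p be the share of eligible patients with an SAE, m the number of implanted screen failures and RR their relative risk; all three are assumptions.

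- All-exposed rate = (35p + m·p·RR) / (35 + m)
- Expected patients with an SAE outside the tables = m·p·RR
- Chance of at least one = 1 − (1 − p·RR)^m
- Share of all patients with an SAE who are left out = m·RR / (35 + m·RR)

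| p | m | RR | All-exposed rate | Expected outside | At least one | Share left out |
|---|---|---|---|---|---|---|
| 10% | 2 | 1 | 3.7/37 = 10.0% | 0.2 | 1 − 0.9² = 19% | 2/37 = 5% |
| 10% | 5 | 2 | 4.5/40 = 11.3% | 1.0 | 1 − 0.8⁵ = 67% | 10/45 = 22% |
| 10% | 15 | 3 | 8/50 = 16.0% | 4.5 | 1 − 0.7¹⁵ = 99.5% | 45/80 = 56% |
| 20% | 15 | 3 | 16/50 = 32.0% | 9.0 | over 99.9% | 45/80 = 56% |

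Over m = 2 to 15 and RR = 1 to 3, the shift in the rate runs from 0 to 6 points at p = 10% and from 0 to 12 points at p = 20%. The range is too wide to serve as an estimate.

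For context, with 35 patients an event of true frequency 2% is seen at least once with probability 1 − 0.98³⁵ = 51%. In a study this small, one or two further serious events in exposed patients are worth counting.

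**The case against.** The case against has several parts, and much of it stands.

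- **The events are not shown to be lost.** A reader might infer that they vanish from the results. The Protocol's listing commitments (Step 3) do not support that. What is shown is absence from tables and rates; a listing gives no count against a denominator.
- **Not every safety set is strictly eligible.** Protocol 10.3 forms the per-protocol set by removing subjects who fail eligibility from the full analysis set, and SAP 6 gives an eligibility violation at enrollment as a major deviation. Both imply that ineligible patients enrolled in error can sit in the main set. This stands, but patients recorded as screen failures remain outside.
- **Risk and labelling are unproven.** A reader might infer that the omitted patients are the highest-risk in-label users. That is plausible for exclusions 3 to 5 (infection, uncontrolled diabetes, cirrhosis or ascites), but the documents give no risk by criterion, the Instructions for Use are not among them, and exclusion 1 matches the contraindication.
- **An eligible cohort is a legitimate target.** Restricting a small descriptive series limits confounding when events are attributed to the device, since infection or cirrhosis can themselves cause serious events. This stands for the endpoints. It does not explain why serious events requested by 5.5 have no planned count.
- **Extending the primary endpoint to screen failures is not cheap.** It would need 90-day chart abstraction with full source verification, beyond the minimal data set of 5.5. This stands, and it is not proposed.

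**Conclusion.** The point holds as a reporting and consistency gap. Implanted screen failures are to have their SAEs recorded under Protocol 5.5, three other sections cast doubt on whether that will happen, and no planned safety table or rate includes them. This sits badly with the aim of detecting unknown side-effects in a real-world series.

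Its size cannot be fixed from the documents. A reader might assume a 20% event rate, 10% to 30% of the series failing exclusions 3 to 5, and 1.5 to 2.5 times the risk in them. The all-treated rate is then 0.9 × 20% + 0.1 × 30% = 21% up to 0.7 × 20% + 0.3 × 50% = 29%, and the reader might conclude that the plan understates risk by 1 to 9 points. The documents do not support this: all the inputs are assumed, and the plan never targets an all-treated rate. With 7 events in 35 patients (20%), the exact 95% interval is 8.4% to 36.9%, which covers the whole of that range.

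The conclusion rests on the text of the sections compared above, not on the illustration. It is a cheap improvement and does not put the eligible-cohort analysis in question.

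**What to change.** 1. **Collection.** Reconcile Protocol 5.5 with 5.4, 6.1.1 and 7.3.1, so that it is plain that deaths and SAEs of implanted screen failures are entered, and where.
2. **Safety set.** Name one set, with one definition, in Protocol 10.3 and SAP 7, 9.3.4 and 9.3.5, and remove or define the full analysis population in SAP 9.3.5.
3. **Supportive output.** Add to SAP 9.3.5 a count and listing of deaths and SAEs, not only SADEs, in all Gentrix-treated patients screened. Show screen failures by exclusion reason next to the ITT column, with the number of patients in each group.
4. **Unchanged.** The primary endpoint stays in the eligible cohort.

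The cost is slight extra data entry for screen failures (none beyond what 5.5 already requires), one extra column and one extra listing. The safety picture may look less favourable.

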#### **5.6** Strategies for Recruitment

The retrospective chart review will include the full consecutive series of patients between 22 years and 80 years old who underwent abdominal wall reconstruction for a hernia with Integra Gentrix® Surgical Matrix during the time period between November 1, 2017, and present (90 days prior). Subjects from that consecutive series will be included in the study based on the defined inclusion and exclusion criteria. Collection of patients' data treated with the Gentrix® Surgical Matrix per routine/standard of care use and in accordance with the Instructions for Use (IFU).

The institutional charts from the study site will constitute the source documents, and data from such charts will be collected using a study-specific eCRF by the site responsible or their designee(s). Each patient should be included in the study only once. Patient screening will rely on manual selection of institutional charts or other means. In these cases, every effort should be made to identify every possible eligible patient. In order to be eligible for the study, patients should meet all of the eligibility criteria.

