#### 5.4 Point of Enrollment & Enrollment Period

There are no physical participants as this is a retrospective study. The requirement for consent being waived, the patients will not provide informed consent to allow use of their data. There is no traditional enrollment period in this study. Data will begin to be collected from the first patient who meets all the eligibility criteria.

This study is anticipated to have a data collection period of one month from initiation of the site until data delivery.

The total expected duration of the study is, therefore, approximately 3 months.

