#### 10.4.2 Measures to Minimize Bias: Randomization and Blinding

This study does not include a randomization or blinding component. When screening subjects for the study, Investigators should offer participation to any/all patients who may meet the inclusion and exclusion.

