#### 8. SAMPLE SIZE DETERMINATION

Subjects from that consecutive series will be included in the study based on the defined inclusion and exclusion criteria, and sample size is not based on hypothesis testing. The planned sample size for this study will be approximately 35 treated subjects.

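### The protocol requires a full consecutive series, but cases are found by manual chart selection and an eligible chart that is never selected leaves no trace, so completeness cannot be verified

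*Protocol*

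**What the plan says.** Protocol 5.6 sets the sampling frame: "The retrospective chart review will include the full consecutive series of patients between 22 years and 80 years old" who had abdominal wall reconstruction for a hernia with the device, from 1 November 2017 to 90 days before data collection starts. Section 6.1.1 repeats it. Inclusion then depends on the eligibility criteria.

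On how cases are found, 5.6 says "Patient screening will rely on manual selection of institutional charts or other means". The other means are not described. It then adds that "every effort should be made to identify every possible eligible patient". Protocol 10.4.2 states that "This study does not include a randomization or blinding component" and that "Investigators should offer participation to any/all patients who may meet the inclusion and exclusion".

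On size, SAP section 8 says "The planned sample size for this study will be approximately 35 treated subjects", as does Protocol 10.2. The SAP adds that "sample size is not based on hypothesis testing". Neither document derives the figure or says what happens if the series yields more or fewer patients.

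**The concern.** In a retrospective single-arm series, who enters the denominator largely determines the result. Here the site searches its own charts by hand, and those charts already contain the post-operative course. If some eligible patients are not found, and being found is related to how they fared, the complication rate is biased. No planned analysis can correct this, because the missing patients are not in the database, and a confidence interval does not cover it.

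The usual protection is an independent count of the cases that should be there. The plan states the goal of completeness but provides no such count. What is at stake is the primary endpoint, which the SAP reports as one proportion and which is meant to confirm the device's continued performance, and also the right to call the series consecutive.

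**Working it through.** **Step 1. Would any planned record reveal an eligible chart that was never selected?**

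- Screening and Enrollment log (Protocol 5.5): screen failures are patients the site has already created on the CRF. A chart never picked is not created, so it is not logged.
- Case books (Protocol 6.1.1): opened for each eligible subject after the chart has been found. They give no list of charts not found.
- Monitoring (Protocol 6.3): one on-site visit after the eCRFs are complete, with 100% verification of collected data against source. This checks the accuracy of included cases. No search for missed cases is stated.
- Device accountability (Protocol 2.2.4): not performed, so there is no implant count to compare with. Traceability (2.2.5) records type, size and lot only as part of the study database.
- Disposition (SAP 9.2.1): starts from subjects under the consent waiver and those screen failed or enrolled, not from all Gentrix hernia cases in the window.
- Enrolled population (SAP 7): defined as all eligible subjects, with nothing against which to test that statement.

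None of the six would show the omission.

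**Step 2. Can the planned size serve as a check?** No. The documents give no event rate, precision target, power or count of eligible cases, so 35 can be neither reproduced nor refuted. A Wald calculation with p = 0.10 and half-width 0.10 gives 1.96² × 0.10 × 0.90 / 0.10² = 34.6, or 35, but neither input is in the documents and the match may be coincidence.

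**Step 3. How far could the primary proportion move?** Suppose x events are reported in 35 patients and m eligible charts were missed. The full-series rate then lies between x/(35 + m), if no missed patient had an event, and (x + m)/(35 + m), if all did. Both x and m are assumptions.

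| Reported | m = 2 | m = 5 | m = 10 |
|---|---|---|---|
| 3/35 = 8.6% | 8.1% to 13.5% | 7.5% to 20.0% | 6.7% to 28.9% |
| 5/35 = 14.3% | 13.5% to 18.9% | 12.5% to 25.0% | 11.1% to 33.3% |
| 7/35 = 20.0% | 18.9% to 24.3% | 17.5% to 30.0% | 15.6% to 37.8% |

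These are extreme bounds, not expectations.

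**Step 4. A milder illustration.** Assume 45 eligible patients with 9 events: 9/45 = 20.0%. Leaving out 10 at random removes 10 × 9/45 = 2 events on average. If the 10 hold 3 events, the report reads 6/35 = 17.1%. If they hold 4, it reads 5/35 = 14.3%.

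**Step 5. Could such a shift be recognised in the results?** No. Under random omission of 10 from 45, the hypergeometric probability that the omitted group holds 3 or more of the 9 events is 31%, and 4 or more, 9%. The exact 95% intervals also overlap heavily: 5/35 gives 4.8% to 30.3% and 7/35 gives 8.4% to 36.9%.

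**The case against.** A reader might infer that the site is free to choose which cases enter. The documents do not support that. Protocol 5.6 and 6.1.1 require the full series, the eligibility criteria decide inclusion, and the sentence on manual selection describes how charts are located. The instruction to make every effort follows directly, and 10.4.2 extends it to any and all patients who may qualify. Leaving out a known eligible patient would be a deviation under Protocol 11.3. All of this stands. But these sentences state an intention and name no list, record or reconciliation that would show whether it was met.

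A reader might also infer that abstraction may stop at 35. No passage says so. In both documents the figure directly follows the statement that patients come from the consecutive series, and expected yield is the natural reading. The statement in Protocol 5.4 that "Data will begin to be collected from the first patient who meets all the eligibility criteria" concerns when collection starts and shows neither selection nor a cap. What remains is that the meaning of 35 is not stated.

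Three further points have weight.

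- The documents do not say that the person locating charts knows the outcomes beforehand; the site may use a designee. The study is unblinded, however, and the outcomes are in the charts, so nothing prevents it.
- The undefined other means could include an operating-room query, and the monitoring plan or data-management plan may contain a reconciliation. Neither plan is among the documents reviewed, so this cannot be confirmed or excluded.
- The numbers in Steps 3 and 4 rest on assumed counts, and in Step 4 the smaller shift is within what chance omission produces. They show that the endpoint is sensitive to missed cases; they are not evidence of bias.

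**Conclusion.** The point holds as a gap in verification. The plan requires a complete consecutive series, relies on manual chart selection or undefined other means at an unblinded site, and keeps no record that would reveal an eligible chart never selected. An incomplete or selected series could be reported as consecutive, and neither monitoring nor analysis as described would detect it.

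Nothing shows that cases will be missed or that selection is intended. The size of any bias is unknown, because it depends on how many eligible charts are missed and on how many events they hold, and the documents give neither. With 35 patients, a few missed charts could matter: under the assumed 3/35, five missed charts leave the full-series rate anywhere from 7.5% to 20.0%. The change is worth making because it is cheap and because the omission cannot be repaired in analysis.

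**What to change.** In Protocol 5.6, replace the sentence on manual selection with a procedure along these lines:

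- Before charts are reviewed for outcomes, the site generates a list of all hernia or abdominal wall reconstruction cases that used an Appendix I SKU, from 1 November 2017 to 90 days before the start of data collection. The source is operating-room, implant or procedure-code records that identify patients. Purchasing records count devices and need not identify patients, so they serve only as a cross-check on the total.
- Every listed case is screened in date order and entered on the Screening and Enrollment log as enrolled or as excluded with the reason.
- The monitor reconciles the log to the list at the visit already planned in 6.3.
- The report shows the flow from all listed cases to those analysed.

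The restriction to hernia and abdominal wall cases is needed because Protocol 2.2 gives other labelled uses for the device, such as prolapse and esophageal repair.

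In Protocol 10.2 and SAP section 8, add that about 35 is the expected yield and that all eligible patients are included whatever the count.

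The cost is one record query at one site, log entries for excluded hernia cases (with the minimal data set of Protocol 5.5 if they are handled as screen failures), and possibly a few more charts to abstract. Patient identifiers can stay at the site, as Protocol 5.7.2 already provides.
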